**Other Pre-specified Outcomes:**

- 1. •Overall survival time [ Time Frame: 30 days ]
  - Overall survival time, defined as time from randomization to death. The time will be censored at the time of last visit for surviving patients
- 2. •Days on intensive care unit (ICU) [ Time Frame: 30 days ]
  - Days on intensive care unit (ICU)
- 3. •Vasopressor dosage [ Time Frame: 24, 48, 72 hours ]

Vasopressor dosage of adrenaline, noradrenaline, vasopressin, and dobutamine at 24, 48,72 h

4. Fluid substitution and fluid balance [ Time Frame: 24, 48, 72 hours ]

Total fluid[ml] substitution and fluid balance [ml] at 24, 48, 72 h

3. Length of hospital stay [Time Frame: up to 1 months]

Days at hospital

4. Mortality [Time Frame: First 72 hours]

The period of occurrence of mortality

### Statistical studies

1) Statistical data processing

2) Comparison and analysis of source data

After data receiving, statistical analysis will be performed using SPSS Statistics software version 22. For quantitative data, the Mann-Whitney Yu non-parametric test and parametric t-test will be performed, and Fisher's non-parametric exact test and  $\chi^2$  parametric test will be performed for qualitative studies. Also, a logistic regression for categorical outcomes and a survival analysis (non-parametric Kaplan-Meier and parametric Cox regression) will be performed.

**Ages:**18 Years and older

**Sex:** All

**Accepts healthy volunteers:** No

Groups	Inclusion criteria	Exclusion Criteria:
ICU patients with ECMO	

• Hemodynamic support with vasopressors

• Procalcitonin level <math>\geq 1</math> ng/ml

• Invasive hemodynamic monitoring

• Written informed content

	

• age <math>< 18</math> years

• acute liver or kidney failure straight before transplantation

• the patient declines participating in the study

ICU patients with septic shock of medical origin	

• Signs of hypoperfusion: serum lactate <math>>2</math> mmol/L, low central venous oxygen saturation (ScvO2) (<math><70\%</math>) or high ScvO2 (<math>>85\%</math>), metabolic acidosis, oligo-anuria,

	

• Patients under 18 years

• Pregnancy (bHCG test positivity)

• Surgical intervention in context with the septic insult

	
high venous-to-arterial CO2-gap (dCO2 >6 mm Hg)
 
 
• Hemodynamic support with vasopressors
 
• Procalcitonin level <math>\geq</math> 1 ng/ml
 
• Invasive hemodynamic monitoring
 
• Written informed content
 
	
New York Heart Association IV heart failure
 
 
• Acute coronary syndrome
 
• Acute haematological malignancies
 
• Immunosuppression, systemic steroid therapy (>10mg prednisolon/day)
 
• Human immunodeficiency virus infection (HIV) and active AIDS
 
• Patients with donated organs
 
• Thrombocytopenia (<20.000/ml)
 
• More than 10%-of body surface area with third degree burn
 

--	---	--

Study will be conducted in accordance with international standards of Good Clinical Practice, Joint Commission International, Scientific Ethics (Helsinki Declaration), as well as the Order of the Minister of Health of the Republic of Kazakhstan April 2, 2018 No. 142 "On approval of the Rules for conducting biomedical experiments, preclinical (nonclinical) and clinical studies, as well as requirements for preclinical and clinical bases". It will also take place according to the recommendations of the Local Ethical Commission at the NSCC. All patients will receive voluntary informed consent of the established sample with permission to use clinical data for scientific purposes. In addition, the study will be strictly controlled by researchers for the absence of plagiarism, falsification and fabrication of data in order to achieve the most ethical conduct of the study. The obtained patient data will be kept strictly confidential, ensuring privacy by strictly limited access to data, de-identification of data and destruction after the end of the study.

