#### Secondary outcomes

1. Ventilator free days (VFD) [Time Frame: 30 days]

Ventilator free days (VFD) in the first 30 days after randomization, where invasive mechanical ventilation (IMV), non-invasive ventilation (NIV) and ECMO are defined as ventilator days. VFD=0, if the patient dies in the first 30 days after randomization

2. Time to extubation from ventilation and explantation from ECMO [ Time Frame: 30 days ]

Time to extubation from ventilation and explantation from ECMO. Death under ventilation and/or ECMO will be analyzed as a competing event. The time will be censored at the time of last visit for surviving patients under ventilation and/or ECMO.

3. Difference of d-dimers [Time Frame: 24, 48, 72 hours]

Comparison to enrollment or between 3 groups at 24, 48, 72 h

4. Difference of Serum lactate [Time Frame: 24, 48, 72 hours]

Comparison to enrollment or between 3 groups at 24, 48, 72 h

5. SOFA-Score [Time Frame: 24, 48, 72 hours]

Sequential Organ Failure Assessment Score at 24, 48, 72 h (values from 6 to 24, where the higher values explain higher disease severity)

6. Serious adverse device effects [Time Frame: 30 days]

Serious complications or malfunctions related to the CytoSorb device

7. Adverse event of special interest: air in the ECMO system [Time Frame: 30 days]

- Unintended air in the ECMO system during operation of the device
- 8. Adverse event of special interest: blood-clotting in the ECMO system [Time Frame: 30 days]
  - Unintended blood-clotting in the ECMO system during operation of the device
- 9. Adverse event of special interest: bleeding complications [Time Frame: 30 days]
  - Major bleeding events

*Patient with septic shock*

- 1. Difference of Cytokine response [ Time Frame: 24-48 hours of septic shock ]
  - Cytokine response: Level of procalcitonin, Level of C-reactive protein, Level of interleukin-1, Level of interleukin-6, Level of interleukin-8, Level of interleukin-10, Level of Tumor Necrosis Factor-  $\alpha$  at 24, 48 hours.

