**Secondary Outcome Measures:**

- 1. Inflammatory reaction [Time Frame: 6 - 24 hours]
  - Level of C reactive protein (CRP), white blood cells and procalcitonin immediately after induction of anesthesia, before initiation of adsorber, 2 hours after initiation of adsorber, at termination of adsorber, 6-12-24 hours after wean of adsorber.
- 2. Difference of serum interleukin-6 level [Time Frame: 48, 72 hours]
  - Comparison to enrollment or between 3 groups at 48, 72 h
- 3. Difference of serum interleukin-1 $\beta$  level [Time Frame: 24, 48, 72 hours]
  - Comparison to enrollment or between 3 groups at 24, 48, 72 h
- 4. Difference of serum interleukin-10 level [Time Frame: 24, 48, 72 hours]
  - Comparison to enrollment or between 3 groups at 24, 48, 72 h
- 5. Difference of serum procalcitonin level [Time Frame: 24, 48, 72 hours]
  - Comparison to enrollment or between 3 groups at 24, 48, 72 h

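### Markers read several times are matched only with two-sample tests; one baseline-adjusted repeated-measures analysis per marker, with a pre-named contrast, would be better

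*Combined protocol and SAP*

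**What the plan says.** The section Statistical studies is the whole analysis plan. For quantitative data: "For quantitative data, the Mann-Whitney Yu non-parametric test and parametric t-test will be performed". It adds Fisher's exact and chi-square tests for qualitative data, and then: "Also, a logistic regression for categorical outcomes and a survival analysis (non-parametric Kaplan-Meier and parametric Cox regression) will be performed". It names no repeated-measures or mixed model, no summary over time, no main time point, no baseline covariate and no significance level.

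The outcome lists set many quantitative outcomes at several times:

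- ECMO secondary outcomes: d-dimers and lactate ("Difference of Serum lactate [Time Frame: 24, 48, 72 hours"), each with the note "Comparison to enrollment or between 3 groups at 24, 48, 72 h", and the "Sequential Organ Failure Assessment Score at 24, 48, 72 h".
- Septic secondary outcomes: IL-1beta, IL-10 ("Difference of serum interleukin-10 level [Time Frame: 24, 48, 72 hours") and procalcitonin at three hours; IL-6 at two ("Comparison to enrollment or between 3 groups at 48, 72 h").
- Other pre-specified outcomes: four vasopressors at 24, 48 and 72 h, and "Total fluid[ml] substitution and fluid balance [ml] at 24, 48, 72 h".
- The ECMO primary outcome: five cytokines before ECMO and at five later times. The septic cytokine response: seven markers at 24 and 48 h.

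Patients are randomized to three groups of 30, planned as 15 on ECMO and 15 with sepsis in each.

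**The concern.** A two-sample t-test or Mann-Whitney test takes one value per patient. Applied to outcomes fixed at 24, 48 and 72 h, it gives a separate test at each hour. This has three consequences.

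First, with no main hour named, a chance difference at any hour can be reported as an effect of the device. Second, if the hours disagree, nothing in the plan says which one answers the question. Third, the plan leaves unused two sources of precision that it already pays for: the other readings from the same patient, and the enrollment value. With 15 patients per cell, an open-label design and results intended to become practical protocols, both the error rate and the precision matter. The ECMO primary outcome has the same gap.

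**Working it through.** **Inputs.** From the documents: three arms, 15 patients per arm in each population, and the reading times above. Not in the documents, so assumed: two-sided 0.05 per test; normal data; equal correlation rho between any two readings of a patient, taken as 0.5, 0.7 and 0.9; a true difference of 0.8 SD for power. The plan gives no error rate, power or effect size, so there is no stated figure to reproduce.

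**Step 1: count of tests.** ECMO secondary: 3 outcomes × 3 hours = 9. Septic secondary: 3 × 3 + 2 (IL-6) = 11. Vasopressors: 4 × 3 = 12. Fluids: 2 × 3 = 6. Total 38 readings from 3 + 4 + 4 + 2 = 13 outcomes. Per pair of arms that is 38 hourly tests against 13 outcome-level tests; over three pairs, 114 against 39. Either way the cut is 38/13 = 2.9-fold. The cytokine outcomes come on top: 5 cytokines × 5 later times = 25 readings for the ECMO primary, and 7 × 2 = 14 for the septic response.

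**Step 2: false differences per outcome, one pair of arms.** With independent readings, 1 − 0.95³ = 14.3%. With correlated readings (simulation, at least 20,000 trials per setting, 15 per arm, t-test at each hour):

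| rho | any of three hours | one test on the three-hour mean |
|---|---|---|
| 0.5 | about 13% | about 5% |
| 0.7 | about 11% | about 5% |
| 0.9 | 8 to 9% | about 5% |

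For an outcome with two readings, such as septic IL-6, the figure is 8.8% (rho 0.5) to 7.3% (rho 0.9).

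**Step 3: how much belongs to hourly testing.** Over all three pairs of arms, nine tests at rho 0.7 give about 25%. Testing only the three-hour mean in the same three pairs still gives about 12%. That remainder comes from comparing three arms and is a separate issue.

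**Step 4: precision, in units of one reading's variance.**

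- Mean of three readings: (1 + 2·rho)/3. At rho 0.7: 2.4/3 = 0.80.
- One reading adjusted for enrollment: 1 − rho². At rho 0.7: 0.51.
- Mean adjusted for enrollment: (1 + 2·rho)/3 − rho². At rho 0.7: 0.80 − 0.49 = 0.31.

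**Step 5: power at rho 0.7, 15 per arm** (noncentral t for the unadjusted single reading and the mean; simulation for the others):

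| Analysis | constant 0.8 SD | fading: 0.8, 0.4, 0 SD |
|---|---|---|
| 24 h reading alone | 56% | 56% |
| three hours, Bonferroni | 57% | 39% |
| mean of three | 66% | 22% |
| 24 h reading, baseline-adjusted | 83% | 83% |
| mean of three, baseline-adjusted | 96% | 46% |

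The fading column follows from the mean effect (0.8 + 0.4 + 0)/3 = 0.4 SD. At rho 0.5 and 0.9 the unadjusted mean has 74% and 59% power for the constant effect. Most of the gain comes from the enrollment value; combining the hours adds to it when the effect persists.

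**The case against.** **The plan does not say in words that it tests hour by hour.** True; this is an inference. A t-test can be paired, and the outcome lists allow a comparison with enrollment. But a paired test within an arm does not compare arms, and no text says that hours are combined. If the sponsor intends to combine them, the same amendment is needed to say so.

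**The count is easily overstated.** A reader might set 114 hourly tests against 13 outcomes and infer a ninefold excess. That multiplies only one side by the three pairs of arms; like for like, the cut is about threefold. Likewise, a reader might charge all of the 25% over three pairs to hourly testing. Step 3 shows that about 12% would remain without it.

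**Error and power are two different complaints.** If any of three hours may count, power for the constant effect is about 75%, above the 66% of the unadjusted mean. That power is bought with an 11% error rate; held to 5% by Bonferroni it is 57%. So the precision argument stands at a fixed error rate, but the plan should not be charged with inflated error and single-reading power under the same decision rule.

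**Averaging is not always better.** This objection stands in full. The documents do not say whether an effect should last or fade. If it fades, the average loses to the 24 h reading, with or without adjustment. The choice of contrast is a choice of what to estimate.

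**One model does not suit every outcome.** This also stands. Fluid totals may be cumulative, and doses of four separate vasopressors are likely to include many zeros, so a log-scale model would not fit them.

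**Conclusion.** The point holds as a recommended improvement. The tests named do not fit outcomes read repeatedly, and the plan has no main hour, no rule for combining hours and no baseline adjustment. Under an assumed two-sided 0.05, 15 per arm and rho between 0.9 and 0.5, the chance of at least one false difference is about 8 to 13% per three-reading outcome and pair of arms, instead of 5%. The size depends on these assumptions; for any correlation below 1 the direction does not.

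The power gain (56% to about 66%, and to about 96% with baseline adjustment, at rho 0.7) rests on a constant 0.8 SD effect and on the enrollment value correlating with later readings as strongly as they do with each other. A reader might infer that the average is the right result for every marker, or that this change settles multiplicity in the trial. The documents support neither: they give no time course for the effect, and the comparison of three arms needs its own rule. The 38 readings counted are secondary or other outcomes; the same gap in the ECMO primary is the stronger reason to act.

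**What to change.** 1. For SOFA and each repeatedly measured laboratory marker, including the ECMO primary cytokines and the septic cytokine response, replace the separate tests by one mixed model with arm, time, arm-by-time and the enrollment (pre-treatment) value as covariate, on the log scale for skewed markers.
2. Name one contrast per outcome as the result before data are seen, for example the average difference over the planned post-baseline times. If an early, fading effect is expected, name an early contrast instead and say why.
3. Show the single times as a time course with confidence intervals, without separate verdicts.
4. Report vasopressor doses and fluids descriptively, or with one pre-named summary per patient (for example the 72 h total for fluids).
5. State how deaths before the last reading enter the analysis, for example as worst rank with one rank test on each patient's summary. Hourly tests do not avoid this problem, since each would compare a different set of survivors.

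Cost: analysis-plan wording and one model per outcome. For markers with a pre-treatment value already planned, no new samples are needed; the documents should confirm that each marker has one. The price is dilution of an effect confined to one hour, which items 2 and 3 limit but do not remove.

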#### **4. Research methods and ethical issues**

Patients before implantation of ECMO and/or patients with sepsis will be enrolled in the study after giving a written, signed informed consent.

The participants will be randomized into 3 groups:

- **Intervention group #1** a cytokine adsorber will be used (30 patients): patients on ECMO – subgroup A; septic patients – subgroup B.
- **Intervention group #2** an extracorporeal hemoperfusion cartridge will be used (30 patients): patients on ECMO – subgroup C, septic patients – subgroup D.

- **Control group #3** without using extracorporeal adsorber (30 patients): patients on ECMO subgroup - E, septic patients - subgroup F.

The investigators will collect demographic, clinical and laboratory data about patients before, during and after the operation

The incidence of early cellular or humoral rejection, length of ventilation, ICU and hospital stay, the use of vasopressors and inotropes in the perioperative period and incidence of perioperative complications and survival will be documented.

The level of cytokines (IL-1, IL-6, IL-8, IL-10, tumor necrosis factor-alfa) and complements before, during and after the use of ECMO, patients with sepsis will be determined if the investigators find relevant difference between the two groups in clinical variables.

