### Study Design

Study Type: Interventional (Clinical Trial)

Estimated Enrollment: 90 Participants

Allocation: randomized

Interventional Model: Parallel assignment

Masking: None (Open Label)

Experimental (subgroups)	Intervention / treatment (device)
Cytokine adsorber filter will be installed into the (hemodialysis or cardiopulmonary bypass (CPB) (15 patients on ECMO)	Cytokine adsorber is a biocompatible, high adsorptive polymer indicated in conditions where cytokine levels are extremely elevated.
Cytokine adsorber filter will be installed into the (hemodialysis or cardiopulmonary bypass (CPB) (15 patients with sepsis)	Cytokine adsorber is a biocompatible, high adsorptive polymer indicated in conditions where cytokine levels are extremely elevated.
Extracorporeal hemoperfusion cartridge will be installed into the (hemodialysis or cardiopulmonary bypass (CPB) (15 patients on ECMO)	Extracorporeal hemoperfusion cartridge is a biocompatible, high adsorptive polymer indicated in conditions where cytokine levels are extremely elevated.
Extracorporeal hemoperfusion cartridge will be installed into the (hemodialysis or cardiopulmonary bypass (CPB) (15 patients with sepsis)	Extracorporeal hemoperfusion cartridge is a biocompatible, high adsorptive polymer indicated in conditions where cytokine levels are extremely elevated.
Control (subgroups)	
No filter will be installed into the ECMO in	

this study group (15 patients)	
No filter will be installed into the patient with sepsis (15 patients)	

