## Outcome Measures

### Primary Outcome Measures

#### *ECMO patients*

1. Difference of Cytokine response [ Time Frame: 6-24 hours ]

Level of pro- and anti-inflammatory cytokines (IL-1, IL-6, IL-8, IL-10, tumor necrosis factor-alfa) before initiation of ECMO, 2 hours after initiation ECMO support, at explantation of ECMO support, 6-12-24 hours after explantation of ECMO support.

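### Cytokine measurement is made conditional on an undefined clinical difference, and the cytokine primary has no lead reading, named contrast or error control

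*Combined protocol and SAP*

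**What the plan says.** **Arms.** Section 4, Research methods and ethical issues: "The participants will be randomized into 3 groups". The Study Design table gives 15 patients per arm in each cohort, for example "No filter will be installed into the patient with sepsis (15 patients". The trial is open label.

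**When cytokines are measured.** The same section says that cytokine and complement levels "will be determined if the investigators find relevant difference between the two groups in clinical variables". Just before this it lists clinical items to be documented, among them "length of ventilation, ICU and hospital stay, the use of vasopressors and inotropes in the perioperative period and incidence of perioperative complications and survival". It does not define a relevant difference or say which two of the three groups are meant.

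**ECMO primary.** Primary Outcome Measures, ECMO patients: "Difference of Cytokine response [ Time Frame: 6-24 hours". The entry is "Level of pro- and anti-inflammatory cytokines", naming five of them. Samples are taken before ECMO, 2 hours after initiation, and then "at explantation of ECMO support, 6-12-24 hours after explantation of ECMO support". No condition is attached.

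**Septic outcome.** The first septic-shock item is also a cytokine response: seven markers at 24 and 48 hours. It carries no primary label, but a heading for secondary outcome measures follows it.

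**Analysis.** Statistical studies: for quantitative data, "the Mann-Whitney Yu non-parametric test and parametric t-test will be performed". Fisher, chi-square, logistic, Kaplan-Meier and Cox methods are named for other data types. No significance level, contrast or multiplicity rule appears.

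**Other biomarkers.** Six secondary outcomes (d-dimers, lactate, IL-6, IL-1beta, IL-10, procalcitonin) may be compared either with enrollment or between the three groups.

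**The concern.** The plan can be read in two ways. They are alternatives, so their consequences do not add up.

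- *Section 4 governs.* Investigators who know the allocation look at clinical differences and then decide whether the primary is measured. A device that lowers cytokines without moving clinical variables could leave its own primary unassayed.
- *The outcome sections govern.* Everyone is assayed, and the primary is a grid of readings with no stated way to reach one conclusion. A nominally significant cytokine result is then likely even if neither device does anything.

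Under either reading, most ECMO sampling times exist only for patients who reach explantation. The plan treats death on ECMO as a competing event for a secondary outcome, but gives no rule for the primary.

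**Working it through.** **1. The plan's own figure.** 6 subgroups x 15 = 3 arms x 30 = 90, which matches the stated enrollment. The plan states no error rate or power, so there is nothing further to reproduce.

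**2. The passages side by side.**

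| Point | Section 4 | Outcome sections |
|---|---|---|
| Are cytokines measured? | If a relevant clinical difference is found | Listed without condition |
| Groups | Two in this sentence, three in the randomisation | Three |
| Criterion | Not defined | None needed |

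Both columns cannot be followed. This part needs no arithmetic.

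**3. Counting contrasts.** Contrasts = markers x times x 3 pairs.

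- ECMO, all post-baseline times (2 h, explantation, 6, 12, 24 h): 5 x 5 x 3 = 75
- ECMO, if the 6-24 hour frame governs: 5 x 3 x 3 = 45
- Septic: 7 x 2 x 3 = 42

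Two of every three pairs compare a device with control: 50, 30 and 28.

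**4. Chance of at least one significant result with no device effect.** The assumptions, none of them in the documents, are two-sided 0.05 per test and normal readings. If tests were independent, 1 - 0.95^k gives 97.9% (75), 90.1% (45), 88.4% (42) and 14.3% (3). Readings in one patient are correlated, so the rates were simulated: three arms of 15, pairwise t-tests, marker/time correlations from 0.3/0.5 (highest rate) to 0.9/0.9 (lowest).

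| Set | Any pair | Device versus control only |
|---|---|---|
| ECMO, 75 | about 41-90% | about 34-81% |
| ECMO, 45 | about 35-79% | about 28-69% |
| Septic, 42 | about 34-77% | about 27-67% |
| One reading, 3 pairs | 12% | - |

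Simulation error is about one to two percentage points.

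**5. Deaths on ECMO.** Explantation and 6, 12 and 24 h after it make 4 of the 5 post-baseline times, and all 3 in the 6-24 hour frame. A patient who dies on ECMO has none of these.

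**6. Check of one workable replacement.** Per cohort: Kruskal-Wallis at 0.05, then pairwise Mann-Whitney only if it is significant, with deaths before the reading sharing the worst rank.

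- Any false positive with no effect and equal deaths of 0-40%: 4.7-4.9%.
- One device working: false claim for the other against control, at most 4.6%.
- Detectable difference at 80% power, no deaths: 1.16 SD, against 1.06 SD for a single t-test at 15 per arm.
- Power at 1.16 SD with 0, 5, 10, 20 and 40% deaths in every arm: 81, 68, 57, 36 and 13%.
- No cytokine effect but deaths of 20/20/40% (devices/control): significant in about 15% of trials.
- Two cohorts at 5% each: 1 - 0.95^2 = 9.75% trial-wide.

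**The case against.** **Two-sample tests are not wrong for three arms.** Pairwise t or Mann-Whitney tests can serve, and several outcomes do mention a comparison between three groups. This stands. The gap is that contrasts and error control are missing; on one reading the cost would be only 12%. The chi-square, logistic and Cox methods can take three arms, so the gap concerns quantitative outcomes.

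**The upper rates are not the chance of a false claim for a device.** A reader might infer a 90% chance of wrongly declaring a device effective. The documents do not support this. They nowhere say that one significant reading means success, and a third of the contrasts compare the devices with each other. Device-versus-control rates are lower, and counting only results with the device lower than control gives about 17-51%, 14-39% and 13-37%. IL-10 has no stated adverse direction, so these last figures are only a lower comparison.

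**The section 4 sentence says if, not only if.** A reader might infer that the primary will not be measured, or try to compute how often the condition would be met. Neither is supported. The sentence may be a leftover, the criterion is undefined, and the listed clinical items are not stated to be the criterion. One of them, rejection, should not arise in the septic cohort, which excludes patients with donated organs. The conditional meaning is still plain, and so is the contradiction.

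**Within-arm comparison.** A reader might infer that change from enrollment will be taken as a device effect. The wording permits that but does not say it, so this is a lesser point.

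**Conclusion.** The concern holds, and it should be settled before any data are seen. Its weight rests on two things in the text: the conditional measurement of an outcome elsewhere declared primary, and the absence of a lead reading with contrasts and error control. If all patients are assayed, some nominally significant cytokine result is expected in roughly 34-90% of trials with no device effect, or 27-81% counting device-versus-control contrasts only, against 12% for one reading with three pairs. These ranges depend on the assumed 0.05 level and correlations. The contradiction and the missing rule for deaths depend on no assumption. That the septic cytokine outcome is primary is inferred from its position only.

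**What to change.** 1. Reconcile section 4 with the outcome sections: delete the condition, state that the cytokine outcomes are assayed in all randomised patients, and refer to the three arms.
2. Before data are seen, name one primary cytokine and one time per cohort, with its time origin. Say whether the septic outcome is primary, and call all other readings supportive.
3. Test each primary with a three-arm test at a stated level, for example Kruskal-Wallis at 0.05, followed by pairwise Mann-Whitney tests only if it is significant. State whether each cohort has its own 5% (about 10% trial-wide) or they share it (2.5% each).
4. State how deaths before the reading are handled. Worst-rank scoring is one option, not a requirement: it needs a marker with a stated adverse direction, tests cytokine-or-death and loses power as deaths rise, so deaths by arm should be reported beside it. An ECMO reading 2 hours after initiation largely avoids the problem, but the 6-24 hour frame must then be amended.
5. For the six secondary biomarkers, replace the either/or wording with a between-arm comparison.

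**Cost.** Items 2 to 5 are wording. Item 1 commits to up to 45 x 6 x 5 = 1,350 ECMO and 45 x 2 x 7 = 630 septic determinations, all already listed. The septic cytokine outcome lists no enrollment sample; one is needed only if baseline adjustment is used, at 45 determinations for one marker. The downsides are fewer confirmatory readings and a detectable difference of about 1.16 instead of 1.06 SD at 80% power if no one dies before the reading.

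### Two unadjusted tests are named for each data type with no rule for which decides, and neither quantitative test uses the pre-ECMO cytokine value already scheduled

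*Combined protocol and SAP*

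**What the plan says.** Statistical studies is the whole analysis plan. It allots methods by type of data. For quantitative variables, "the Mann-Whitney Yu non-parametric test and parametric t-test will be performed". For categorical variables it names "Fisher's non-parametric exact test" together with chi-square. It then adds: "Also, a logistic regression for categorical outcomes and a survival analysis (non-parametric Kaplan-Meier and parametric Cox regression) will be performed". It gives no check of distribution, transformation, covariate, expected-count rule, significance level or rule for the case where the two tests differ. No other section supplies one.

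The primary outcome for ECMO patients is quantitative: "Level of pro- and anti-inflammatory cytokines (IL-1, IL-6, IL-8, IL-10, tumor necrosis factor-alfa) before initiation of ECMO", then 2 hours after the start of support, at explantation, and 6, 12 and 24 hours after explantation. A pre-treatment value is therefore scheduled in all three arms. The first outcome under Patient with septic shock lists procalcitonin, CRP and five cytokines at 24 and 48 hours only. The Study Design table in section 4 puts 15 patients in each arm-by-population cell.

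**The concern.** The primary cytokine comparison can produce two p-values, and nothing fixed in advance says which one carries the conclusion. In an open-label trial that choice would be made with the data in view. If cytokines are right-skewed, a t-test on raw values is driven by a few extreme patients, and it can miss a difference that a rank test or a log-scale analysis finds.

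The second half of the problem is what both tests leave out. Neither is adjusted for the pre-ECMO level, the obvious covariate in a small trial. Neither is planned with a confidence interval for the size of the effect.

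**Working it through.** **The plan's own figure.** Enrollment is 90 (3 arms of 30; 15 per population within each arm). No alpha, power, effect size or SD is given, so 90 cannot be reproduced, and it is not judged here.

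**Inputs.** From the documents: 15 per cell, the pairs of tests and the pre-ECMO sample. Assumed: two-sided 5%; log-normal cytokines with log-SD 1, 1.5 or 2; baseline correlations of 0.3, 0.5 and 0.7 on the log scale.

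**Reference effect.** A difference of 1.06 log-SD gives the log-scale t-test 80% power at 15 v 15: noncentrality = 1.06 × √(15/2) = 1.06 × 2.739 = 2.90 on 28 degrees of freedom. As a ratio this is exp(1.06 × log-SD): exp(1.06) = 2.9, exp(1.59) = 4.9, exp(2.12) = 8.3. The implied ratio therefore grows with the skew, so a fixed two-fold difference is shown as well.

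**Simulation, 15 v 15, at least 20,000 replicates per scenario.**

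| log-SD | ratio at 1.06 log-SD | raw t-test power | Mann-Whitney power | log-scale t-test power | exactly one of raw t / Mann-Whitney significant | same, fixed two-fold | same, no effect |
|---|---|---|---|---|---|---|---|
| 1 | 2.9 | 60% | 77% | 80% | 22% | 19% | 3.9% |
| 1.5 | 4.9 | 40% | 77% | 80% | 40% | 15% | 4.5% |
| 2 | 8.3 | 26% | 77% | 80% | 53% | 12% | 4.7% |

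These figures move by a point or two with the version of Mann-Whitney used (exact or large-sample). At log-SD 0.5 with no effect, disagreement is 2.8%. Disagreements under an effect run almost entirely one way: at log-SD 1.5 and 1.06 log-SD, Mann-Whitney alone is significant in 37.8% of trials and the t-test alone in 1.6%. Significance in opposite directions occurred in 0.0% of the log-normal comparisons checked. Larger groups do not remove the disagreement: at 30 v 30, log-SD 1.5 and a ratio of 0.33, it is 38.6%.

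**Type I error.** Success on either test gives 5.4% to 7.1% per comparison across the log-normal scenarios, at 15 and 30 per arm.

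**Gain from the baseline value.** ANCOVA on the log scale reduces the residual SD by the factor √(1 − ρ²).
- ρ = 0.3: factor 0.954, standardised difference 1.06/0.954 = 1.11
- ρ = 0.5: factor 0.866, standardised difference 1.22
- ρ = 0.7: factor 0.714, standardised difference 1.48

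Simulated power is about 82%, 88% and 97%. The noncentral t formula on 27 degrees of freedom, which ignores chance baseline imbalance, gives 83%, 90% and 97%.

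**Fisher v chi-square, exact enumeration, 15 v 15.** With no difference, at event rates between 16% and 40%, Fisher rejects in 1.4-1.7% and uncorrected chi-square in 4.3-5.5%. (16% and 40% are the mortality figures that section 3 quotes for sepsis and septic shock.) For 40% v 20%, power is 11% v 23% and the tests disagree in 12.1% of trials. For 40% v 10%, power is 33% v 51% and they disagree in 18.5%.

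**The case against.** The sentence labels each test parametric or non-parametric, so it can be read as a list from which the analyst picks to suit the data. That is a fair reading, but the rule for picking is then what is missing.

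The plan also contains Mann-Whitney, which loses little to the log-scale t-test (77% v 80%). Listing a weaker test beside it does not in itself discard information. Power is lost only if the raw t-test is the one relied on, and the plan does not say that it will be. This stands. The case for change therefore rests on the missing rule and the unused baseline, not on a certain loss of power.

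The tests might also be applied to changes from baseline. The plan does not say so. A change score has SD factor √(2(1 − ρ)), that is 1.18, 1.00 and 0.77 at ρ = 0.3, 0.5 and 0.7, which is worse than ANCOVA at each value.

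A reader might infer that both tests fall on every outcome, or that the trial will often give opposite answers. The documents support neither. Overall survival and time to extubation or explantation have other methods. Disagreement means one p-value below 0.05 and one above, not effects in opposite directions. How often that happens depends on a spread and an effect that the documents do not give.

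**Conclusion.** The point holds in a limited form. Two unadjusted tests are named per data type with no deciding rule, and the quantitative pair leaves the scheduled pre-ECMO value unused. The disagreement rates of 22%, 40% and 53% rest on log-normality, log-SD 1 to 2 and true ratios of 2.9 to 8.3. With a two-fold difference they fall to 19%, 15% and 12%, and with no effect to about 3-5%. Type I inflation is small, about 5-7% per comparison, and would not by itself justify the change. The stronger ground is that a better single analysis is available from ECMO data already planned. Its advantage over Mann-Whitney runs from about 5 points of power (82% v 77%) to 20 points (97% v 77%), depending on the assumed baseline correlation.

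**What to change.** **ECMO primary cytokines.** Replace the pair of tests with one decisive analysis: ANCOVA of the log value with the log pre-ECMO value as covariate, reporting ratios of geometric means between arms with 95% confidence intervals. Label Mann-Whitney as sensitivity only.

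**Sepsis markers.** Use the same model for IL-6, IL-1 beta, IL-10 and procalcitonin, for which Secondary Outcome Measures mentions comparison with enrollment. For IL-8, TNF-alpha and CRP, use it only once an enrollment sample is confirmed. CRP is timed from the start of the adsorber, which is undefined for controls.

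**Binary outcomes.** Name one test in advance. The choice is a trade-off: Fisher is conservative at 15 per cell, while uncorrected chi-square sits close to 5% but slightly exceeds it at some event rates.

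**Cost.** For ECMO this is SAP wording, since the baseline sample is already scheduled. However, the sentence in section 4 that makes cytokine measurement conditional on a clinical difference must be reconciled with the primary outcome. For sepsis, some samples may need to be added. Values below the detection limit need a stated substitution rule, and the result is a ratio rather than a difference in means. The change does not settle multiplicity across cytokines, time points and pairs of arms, which needs its own rule.
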